#### 9.3.2. Primary Endpoint Analysis

The primary endpoint analysis will be a Bayesian  $E_{max}$  model applied to results from an MMRM analysis.

Change from baseline in body weight at Week 12 will first be analyzed using Estimand 1 and an MMRM model (as per Section 9.3.1.1). The MMRM model will be fitted to the change from baseline at all post-treatment dosing timepoints up to Week 12 (ie, Weeks 4, 8, and 12) using the Censored analysis set. Additional terms for type of therapy [ie, platinum or not] and type of cancer will be fitted in the model. Least squares means (and 90% CIs) and mean differences versus placebo (and 90% CIs and p-values) will be provided.

A Bayesian  $E_{max}$  model will then be fitted to the Week 12 LSmeans and SEs from the MMRM analysis. The predicted  $ED_{50}$  for the compound ( $P_{50}$ ) is currently ~150 mg Q4W dose, based on latest data for the compound (this may be updated as new data become available). Prior distributions for the placebo response ( $E_0$ ), the difference in response (difTarget) between the highest dose (400 mg) and placebo, and the residual standard deviation (*sigma*) are:

 $E_0$ : An informative meta-analytic predictive prior, based on historical results from internal and external studies, robustified by the inclusion of a weakly informative component to handle any possible prior-data conflict, will be used for the placebo change from baseline at Week 12. This will be approximated by a t-distribution with a mean of -0.58 kg, an SD of 1.84 kg and 3 degrees of freedom. If additional relevant data become available during the study, a sensitivity analysis may be performed by incorporating the new data, using the same approach as above. Further details on the prior derivation will be given in the statistical analysis plan (SAP).

*difTarget*: A vague t-distribution will be used for the 400 mg placebo-corrected change from baseline at Week 12 with a mean of 0, a SD equal to 10 times the predicted standard deviation (ie, 49 kg) and 5 degrees of freedom.

*sigma*: A uniform prior will be used, with a range we are confident will include the population value. A lower bound of 0.49 kg and an upper bound of 49 kg will be used.

The posterior medians and 90% credible intervals (5th and 95th percentiles of the relevant posterior distribution) will be reported for each randomized dose (including placebo) and their differences relative to placebo. If the  $E_{max}$  model cannot be fitted to the data, or the data do not support a dose-response, the model may be simplified, or the analysis may not be performed and the primary results for the study will be based on the MMRM results at Week 12. More details on how this will be assessed will be described in the SAP. No adjustments will be made for multiplicity.

#### 9.3.3. Secondary Endpoints Analysis

Endpoint	Statistical Analysis Methods

 
Change from baseline in each of the physical activity and gait endpoints at Week 12:
 
Moderate to vigorous physical activity time;
 
Sedentary activity time;
 
Non sedentary activity time;
 
Total vector magnitude;
 
Mean activity level during M6min;
 
Mean gait grand;
 
	Change from baseline in physical activity and gait endpoints will be analyzed separately using Estimand 2 and an MMRM model (as per Section 9.3.1.1). The MMRM model will be fitted to the change from baseline at all post-treatment timepoints up to Week 12 using the Censored analysis set.

 
Mean gan speed,
 
95th percentile gait speed.
 
	Least squares means (and 90% CIs) and mean differences versus placebo (and 90% CIs and p values) will be provided. No adjustments will be made for multiplicity.

 
Change from baseline in each of the FAACT sub-scale scores at Week 12:
 
FAACT-ACS;
 
FAACT-5IASS.
 
	Change from baseline in FAACT sub-scale scores will be analyzed separately using Estimand 3 and an MMRM model (as per Section 9.3.1.1). The MMRM model will be fitted to the change from baseline at all post-treatment timepoints up to Week 12 using the Censored analysis set.
	Least squares means (and 90% CIs) and mean differences versus placebo (and 90% CIs and p values) will be provided. No adjustments will be made for multiplicity.

 
Change from baseline for each of the questions from the CRCSD at Week 12:
 
Anorexia/appetite;
 
Nausea and vomiting;
 
Fatigue.
 
	Change from baseline in questions from the CRCSD will be analyzed separately using Estimand 4 and an MMRM model (as per Section 9.3.1.1). The MMRM model will be fitted to the change from baseline weekly averages at all post-treatment timepoints up to Week 12 using the Censored analysis set.
	Least squares means (and 90% CIs) and mean differences versus placebo (and 90% CIs and p values) will be provided. No adjustments will be made for multiplicity.
Incidence of adverse events, safety laboratory tests, vital signs and ECG abnormalities.	All safety analyses will be performed on the safety population. The safety data will be summarized in accordance with Pfizer Data Standards. All safety data will be summarized descriptively through appropriate data tabulation, descriptive statistics, categorical summaries, and graphical presentations, as appropriate.
	Part B safety data will be reported once all applicable participants have completed Part B of the study. More details will be provided in the SAP.

## 9.3.4. Tertiary/Exploratory Endpoints Analysis

The analysis of exploratory endpoints will be detailed in the SAP.

#### 9.3.5. Other Analyses

Selected data collected at Screening may be reported. These data may include demographic data, concomitant medications, GDF-15 concentrations, height, weight, BMI, and ECOG PS. In addition, a subset of medical history data will be reported; this may include type and stage of cancer, where feasible. Other data collected at Screening that are used for inclusion/exclusion criteria, such as laboratory data, will be considered source data, and will not be required to be reported, unless otherwise noted.

As permitted by data, and determined by the sponsor, the PK/PD relationship between serum ponsegromab concentration and the effect on primary, secondary and/or tertiary endpoints may be explored using a population PK/PD approach. The population PK/PD analysis, if conducted, will be reported in a separate report.

Up to 40 exit interviews will be conducted by telephone at Week 12 or early discontinuation. Interviews will be conducted by trained moderators and are anticipated to be approximately 60 minutes in duration. Using the transcripts and interviewer field notes, dominant trends will be identified in each interview and compared across all the interviews to describe the participant experience with a focus on the themes or patterns in the way the treatment experience is described, and the importance of any improvements reported. Following the analysis, a comprehensive summary report that fully describes the study objectives, methods, participants and results of the qualitative interviews will be prepared and reported separately from the CSR.

Pharmacogenomic or biomarker data from Retained Research Samples may be collected during or after the trial and retained for future analyses; the results of such analyses are not planned to be included in the CSR.

CT scans will be collected, retained, analyzed for tumor burden, skeletal muscle, adipose tissue, and may be used for additional research related to the study intervention(s) and cancer cachexia. The results of such additional research analyses may not be included in the CSR.

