#### Table 1. Schedule of Activities for Part A Double-Blind

Visit Identifier	Screening				F	F/U Part A	ED Part A				
Abbreviations used in this table may be found in											
Appendix 13											
Week #			4	5 b,c	8 d	9 c,e (PK	10 c,f	11 c,e (PK	12	16	
						substudy		substudy			
Day -relative to start of study intervention (Day 1)		1	29	36	57	64	71	78	85	113	
	-28 to -7										
Visit Window (Days)			±3	-3/+7	±3	±2	$\pm 7/\pm 3^{f}$	±2	±2	+7	
Retained research samples for biomarkers (Prep B 1.5 &		Х							Х		Х
Prep B 2.5) r											

a. All participants, regardless of proceeding with the optional OLT period (Part B), will complete the Week 12 visit. Participants proceeding with the optional OLT period (Part B) will complete all Week 12 study procedures before receiving the first dose of OLT study intervention. Transportation to and from the study site may be provided for study participants for Part A visits, as permitted by the country, study site, and participant.

b. The Week 5 visit is considered an optional visit to collect PK and GDF-15 samples as well as measurement of weight and SAE/AE monitoring based upon participant availability. It will not be considered a protocol deviation if the participant is unable to make this visit.

c. The PK and PD assessments at Week 5 and 10, as well as Week 9 and 11 in PK sub-study only may be conducted at participant's home or current residence if it is feasible to be performed by the site for flexibility of participant.

- d. The investigator and participant must decide at the Week 8 visit if they wish to continue to the optional OLT (Part B).
- e. Visits at Weeks 9 and 11 are only applicable for participants enrolled in PK sub-study.
- f. For participants in PK substudy, visit window for Week 10 is ±3 days
- g. All physical exams (full and abbreviated) will include an assessment for ascites and/or edema. In addition, ascites and/or edema will be captured as an AE on the AE CRF. See Section 8.3.1.

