#### Table 1. Schedule of Activities for Part A Double-Blind

Visit Identifier	Screening			Part A: Double-Blind a F/U							ED Part A
Abbreviations used in this table may be found in	_										
Appendix 13											
Week #			4	5 b,c	8 d	9 с,е (РК	10 c,f	11 c,e (PK	12	16	
						substudy only)		substudy only)			
Day -relative to start of study intervention (Day 1)		1	29	36	57	64	71	78	85	113	
	-28 to -7										
Visit Window (Days)			±3	-3/+7	±3	±2	±7/±3 f	±2	±2	+7	

1. Data will be captured using the electronic PRO device at the clinic and should be completed by the participant at the beginning of the visit before any medical procedures or interactions with the medical staff takes place (as much as practically possible). See Section 8.2.2.

m. Data will be captured using the electronic PRO device either at home or at the clinic. Measured immediately at the end of the 7-day consecutive monitoring period for Screening (at home), Week 8 (approximately Day 63 at home), Week 10 (approximately Day 77 at home), and Week 12 (approximately Day 85 at the clinic). The Week 12 assessment is to be collected prior to the first dose of study intervention for participants proceeding with Part B OLT. See Section 8.2.2.

 Measured during Screening, Week 8 (period of Week 8-9) and Week 12 (period of Week 10-12) for a minimum 7 days, using the electronic device at home. See Section 8.2.3.

- o. Phone Interview will be conducted by the vendor within the 10 business days following the Week 12 visit, or at ED, if feasible. See Section 8.2.2.
- p. All CT scans will need to include chest, abdomen, and pelvis to be acceptable for this study. If a SOC CT scan was performed within 3 weeks prior to the Screening visit, then a CT scan at screening is not needed. If a SOC CT scan is being performed at the Week 12 visit, between Weeks 10-12 or within 7 days after the Week 12 visit as part of SOC, then an additional CT scan is not needed. Similarly, if SOC CT scan is performed 2 weeks prior or 7 days after the ED visit, then an additional CT scan is not needed. The RECIST 1.1 categorization (Appendix 11) is to be entered in the CRF after each scan. See Section 8.3.7.

q. If not collected on the designated collection day, collect at the next available time point when biospecimens are being collected in conjunction with a participant visit.

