#### 4. STUDY DESIGN

#### 4.1. Overall Design

This is a Phase 2, randomized, double blind, placebo-controlled study of the efficacy, safety, and tolerability of three different doses of ponsegromab compared to matching placebo in patients with NSCLC, CRC, or PANC, receiving standard of care (which may include

systemic therapy), who have elevated levels of GDF-15 and cachexia. The double-blind period is followed by an optional open-label extension period.

The Screening visit will occur no more than 28 days and no less than 7 days, prior to Randomization. The 7-day minimum duration between Screening and Randomization visits will ensure that the GDF-15 results are available to inform the investigator's assessment of eligibility and the 7-day collection of PRO and physical activity data. Following the Screening period to confirm eligibility, approximately 168 study participants, who meet the entry criteria, will be randomized to study intervention (one of 3 dose groups of ponsegromab or matching placebo) and will be stratified by treatment with or without platinum-based chemotherapy (see Appendix 12), which is known to induce GDF-15 and therefore may impact the response to ponsegromab treatment. The 12-week double-blind dosing period (Part A) will consist of a total of 3 doses administered Q4W SC.

A PK substudy will be conducted in approximately 36 of the approximately 168 participants (approximately 9 in each treatment group in Part A). Up to 3 additional PK and PD samples (two samples during Part A and one sample during Part B, if relevant), will be collected in these participants at timepoints during the study outlined in Sections 1.2 schema and 1.3 SoA.

On completion of Part A, participants will have the opportunity to enter an optional OLT period (Part B) consisting of ponsegromab 400 mg Q4W SC for up to 1 year. The investigator and participant must decide at the Week 8 visit if they wish to continue to the optional OLT period.

Participants opting to continue to the OLT period will receive their first dose of open-label ponsegromab 400 mg at the Week 12 visit, which is the last visit of the double-blind portion. Upon completion of the OLT period, there will be a follow-up visit (Week 72) which is to occur 56 to 63 days post last dose of study intervention.

Participants who do not proceed with the optional OLT period are to complete the Week 12 visit and a follow-up visit at Week 16.

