# 8.2.2.7. Qualitative Exit Interviews

Qualitative exit interviews with a selected group of English-speaking participants (up to 40) at selected sites will be conducted by telephone at the end of Part A, as indicated in the SoA. The interviews will be conducted by trained moderators, that are not part of study site staff, will be audio recorded and transcribed, and are anticipated to be approximately 60 minutes in duration.

The transcripts and interviewer field notes will be used to examine changes in symptoms and impacts experienced over the period of study duration, to describe treatment experience, and the importance of any improvement reported by the study participants. Following the analysis of the qualitative data, a summary report that describes the study objectives, methods, participants, and results of the qualitative interviews will be reported separately from the CSR.

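### Table 1 footnotes a and o give conflicting times for the exit interview in participants entering Part B; under footnote o it follows open-label dosing, and its themes are pooled with the rest

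*Protocol*

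**What the plan says.** The protocol describes the timing of the exit interview in four places.

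- Table 1 marks it in the Week 12 column. Footnote a says that participants continuing to Part B "will complete all Week 12 study procedures before receiving the first dose of OLT study intervention".
- Table 1 footnote o, which is specific to the interview, reads: "Phone Interview will be conducted by the vendor within the 10 business days following the Week 12 visit, or at ED, if feasible".
- Section 8.2.2.7 says that the interviews "will be conducted by telephone at the end of Part A, as indicated in the SoA", so it defers to Table 1.
- Section 9.3.5 says that "Up to 40 exit interviews will be conducted by telephone at Week 12 or early discontinuation". It then compares the dominant trends across all interviews.

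On dosing, Section 4.1 states: "Participants opting to continue to the OLT period will receive their first dose of open-label ponsegromab 400 mg at the Week 12 visit". This applies to all four Part A arms, placebo included.

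Neither Section 8.2.2.7 nor Section 9.3.5 limits recall to the period before that dose, or separates interviews by Part B entry or by date relative to the dose. The SAP sets out no analysis of the interviews.

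**The concern.** The interviews are held at the end of Part A to learn how symptoms changed, what treatment was like and how much any improvement mattered. A participant interviewed after the Week 12 visit who has entered Part B has already had a 400 mg dose and knows that it is active drug. If that participant was on placebo in Part A, the account may contain a first experience of ponsegromab. When these interviews are pooled with those of participants who had no open-label drug, the reader of the summary report cannot tell which themes belong to the blinded period.

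The protocol guards against this elsewhere. For the PGI-S and PGI-C items on physical activity and walking, footnote m says: "The Week 12 assessment is to be collected prior to the first dose of study intervention for participants proceeding with Part B OLT". Footnote o carries no matching rule for a conversation of about an hour on treatment experience.

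**Working it through.** The plan gives no figure to reproduce here. The check is a comparison of the timing rules, followed by simple arithmetic.

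**1. Can both footnotes be met?** The interview is a Week 12 procedure (Table 1). Footnote a requires it before the open-label dose. That dose is given at the Week 12 visit (Section 4.1). Footnote o places the interview after that visit. Read literally, no Part B entrant can satisfy both. If footnote o is taken as the specific rule that overrides footnote a, the contradiction goes, but every Part B entrant interviewed after the visit is then interviewed after dosing.

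**2. How long after dosing?** Ten business days are two working weeks, which is 14 calendar days from any weekday start, ignoring holidays. With the Week 12 visit on Day 85, the window closes at Day 85 + 14 = Day 99. This is a maximum; the interview could take place the next day.

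**3. Could drug be acting in that window?** Section 2.2.1.3 gives a median time to peak unbound ponsegromab of 2.25 to 7.00 days after a single dose in healthy participants (3 to 300 mg groups), which lies inside 14 days. Section 4.3 expects 400 mg to suppress unbound GDF-15 for 4 weeks in more than 90% of patients, from preliminary simulations. Both concern drug level or a biomarker. Neither shows how soon a participant would notice a change in symptoms.

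**4. How many interviews?** Let p be the share of interviewees who enter Part B. The documents do not give p, so the values below are assumptions. They also assume that all 40 permitted interviews take place, all after the visit, with interviewees spread evenly over the four arms (1:1:1:1, Section 9.5).

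Interviews after an open-label dose = 40 × p. Of these, former placebo = 40 × p ÷ 4.

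| Assumed p | After open-label dose | Of these, former placebo |
|---|---|---|
| 0% | 0 | 0 |
| 25% | 10 | 2.5 |
| 50% | 20 | 5 |
| 75% | 30 | 7.5 |
| 90% | 36 | 9 |
| 100% | 40 | 10 |

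Forty is a cap. Interviews held at early discontinuation from Part A are not affected, nor are those of participants who finish Part A without entering Part B. Both lower p.

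**The case against.** The strongest reply is that the interviews carry little inferential weight. They cover up to 40 English-speaking participants at selected sites, are analysed by theme with no arm comparison, estimand or test, and are reported separately from the CSR. Sections 8.2.2.2 and 8.2.2.3 name PGI-S and PGI-C, not the interviews, as the anchors for meaningful within-individual change. This stands, and it limits the importance of the point. A reader might infer that a treatment contrast is blurred or an efficacy result weakened; the documents plan no contrast from the interviews, so that does not follow.

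A second reply is that a specific footnote may qualify a general one. Footnote p does so when it accepts a standard-of-care CT within 7 days after the Week 12 visit, and Section 8.2.2.7 points to Table 1. This is a fair reading of which rule governs, but it confirms that the interview comes after dosing.

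Third, the interview guide is not among the documents and may already limit recall to Part A. If so, part of the concern falls away. It would not remove the influence of knowing that one is now on active drug.

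A reader might also infer that Part A is unblinded. The documents do not say that Part A assignment is disclosed on entering Part B. What the participant knows is the current treatment.

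Finally, the tempting remedy is to hold the interview in the week before the Week 12 visit. That week is the 7-day recall period of FAACT, PROMIS-Fatigue and PGI-S, and the seven diary days averaged for the Week 12 CRCSD (SAP Section 3.2.3). A long conversation about symptoms could prime those answers, some of them secondary endpoints, and only in Part B entrants. Nor would it remove the expectation of participants who chose open-label treatment at Week 8. This objection stands in full.

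**Conclusion.** The point holds as a minor one. The two footnotes conflict for Part B entrants. Following footnote o places their interviews up to 14 calendar days after a 400 mg open-label dose, and the planned synthesis does not distinguish them. Accounts of Part A may therefore include open-label experience and knowledge of current active treatment.

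The size is uncertain: 0 to 40 interviews overall and 0 to 10 from former placebo participants, with about 20 and 5 at an assumed 50% uptake and even representation of arms. The documents give no basis for saying that most interviews are affected. That participants would notice a symptom effect within the window is plausible from the drug-level and GDF-15 figures, but not shown. No primary or secondary result depends on the interviews.

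**What to change.** 1. Reconcile footnotes a and o of Table 1, so that one states plainly when the interview takes place relative to the first open-label dose.
2. In Sections 8.2.2.7 and 9.3.5, record the date of each interview against the date of that dose, and direct the questions to the period before the Week 12 dose.
3. In Section 9.3.5, report interviews held after an open-label dose separately from the Part A themes.
4. Leave the interview after the Week 12 patient-reported outcome assessments.

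The cost is a few lines of protocol text, a line in the interview guide and one date comparison per interview. Where interviews have already been held, the questions can no longer be changed, but items 1 and 3 and the date classification need no further contact with participants. The downside is fewer interviews in each reported group: at an assumed 50% uptake, about 20 after and 20 without an open-label dose instead of 40 together.

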## 9.4. Interim Analyses

Interim analyses may be performed to assess efficacy and/or safety after at least approximately 25% of the planned participants, ie, approximately 30 participants, complete their study participation through Week 12 of the study. Interim analysis results may be used for decisions regarding stopping for futility, stopping for early success, conducting a sample size re-estimation, or adapting the study after the interim analysis. Participants may be discontinued from the study intervention/study as a result of the interim analysis, as described in Section 7.

Before any interim analysis is performed, the details of the objectives, decision criteria, dissemination plan, and method of maintaining the study blind (if applicable) as per Pfizer's SOPs will be documented and approved in an IRC charter. In addition, the analysis details will be documented and approved in the SAP.

Following completion of Part A (PCD), the data will be analyzed and reported in the main CSR. The results for Part B will be reported separately at the end of Part B.

